3 STUDY OBJECTIVES AND DESIGN

3.1 Study Objectives

The primary objective of the study is to confirm the clinical benefit of fluciclovine (¹⁸F) PET/CT in affecting management decisions in subjects with biochemical recurrence (BCR) being considered for radical salvage treatment (with curative intent).

The secondary objectives of the study are

 To assess possible improvement in outcome of radical salvage treatment based on fluciclovine (¹⁸F) PET/CT being included in the assessment

Date: 10OCT2018 Version: Amendment 1 Final

- To assess the PSA threshold for positive lesion detection by fluciclovine (¹⁸F) PET/CT in BCR
- To assess the safety of fluciclovine (¹⁸F) injection in subjects undergoing PET/CT

[figure not shown]
3.2 Study Design

This will be an open-labelled, multi-centred study in the United Kingdom.

The study group will include up to 180 subjects with a diagnosis of BCR of previous radically treated prostate cancer (PCa), and who are being considered for radical salvage therapy.

Subjects will have a fluciclovine (¹⁸F) PET/CT scan in addition to standard work-up for radical salvage therapy. The clinical utility of fluciclovine (¹⁸F) PET/CT will be assessed by recording changes to the recommended management plan influenced by the scan result.

The summary flow chart of the study design is as follows:

3.3 Visit Structure

The visit structure and scheduled assessments are detailed in Appendix A: Schedule of study procedures of the protocol.

Date: 10OCT2018 Version: Amendment 1 Final

3.4 Sample Size

For the primary objective of treatment change evaluation, a minimum of 171 subjects with complete primary endpoint data will be required to allow for a width of +/-6% in a two-sided 95% confidence interval (CI). This is based on the conservative assumption that 20% of subjects will have a treatment change, as fluciclovine (¹⁸F) PET/CT has been shown to upstage 25.7% of subjects with recurrent prostate cancer, and also based on the management change studies reported on choline PET/CT. The aim is to recruit 180 subjects for this trial, based on an anticipated primary endpoint drop-out rate of 5%.

3.5 Changes from the Protocol Planned Analysis

The protocol specified "Improvement in outcome of radical salvage treatment based on fluciclovine (¹⁸F) PET/CT being included in the assessment" as a secondary endpoint. This was to be assessed based on PSA and radiological response. Due to lack of data being recorded for radiological response this definition was not used, treatment response was instead assessed using PSA only (see section 5.4.2.1.).

4 STUDY SUBJECTS

4.1 Analysis sets

The list of subjects to be included in each of the analysis set is to be agreed between the Syne qua non statistician and Blue Earth Diagnostics once all study data are available and prior to database lock.

Enrolled Set: All subjects who entered screening.

Safety Analysis Set (SAF): All subjects who have been included in the database and have been administered fluciclovine (¹⁸F) will be included in the Safety Analysis Set (SAF).

Full Analysis Set (FAS): All subjects enrolled who have had a fluciclovine (¹⁸F) PET/CT scan will be included in the Full Analysis Set (FAS).

Evaluable Analysis Set (EAS): All subjects from the FAS who have an intended treatment management plan completed and a revised management plan page completed will be included in the Evaluable Analysis Set (EAS).

Per Protocol Set (PPS): All subjects in the EAS without major significant deviation following review of the protocol deviation list.

4.2 Disposition of Subjects

The number and percentage of all subjects enrolled, included in each analysis set, who completed the study and who prematurely withdrew, including a breakdown of the primary reasons for withdrawal, will be presented.

All enrolled subjects will be listed indicating their membership to the evaluable analysis set along with the reason for exclusion.

Completion and withdrawal information will be listed, including individual reasons for withdrawal.

Date: 10OCT2018 Version: Amendment 1 Final

4.3 Protocol Deviations

Failed inclusion criteria and failed exclusion criteria will be listed for screening failures.

The number and percentage of subjects within each deviation category will be presented by deviation type (Major Significant, Major or Minor) and by site and overall. The deviation category and type will be provided by Blue Earth Diagnostics. All protocol deviations will be listed.

4.4 Background and Demographic Characteristics

4.4.1 Demographic and Baseline Characteristics

Demographic characteristics (age, ethnic origin and race collected at Screening), body measurements (height, weight collected, and BMI derived at Visit 2) will be summarised for the enrolled set, FAS, EAS and PPS populations.

Body mass index (BMI) is calculated as (weight (kg)/height (m)²).

Individual demographic characteristics and body measurements data will be listed.

4.4.2 Medical History

Medical history events will be coded using the Medical Dictionary for Regulatory Activities (MedDRA) version 18.1.

The number and percentage of subjects from the FAS with previous medical history and current events will be tabulated by system organ class (SOC), preferred term (PT). SOCs will be ordered in decreasing frequency of the total number of subjects with medical history events reported in each SOC and PTs will be ordered within a SOC in decreasing frequency of the total number of subjects with each medical history event. This table will be repeated for all events, regardless of whether previous or current events.

All medical history events will be listed.

4.4.3 Prostate Cancer History

Details of prostate cancer history will be summarised for subjects from the FAS, and will consist of:

- Time since initial diagnosis (months), calculated as [12*(date of informed consent date of initial prostate cancer diagnosis + 1)/365.25]
- TNM stage: Pathological TNM stage if available, otherwise Clinical TNM stage. A summary for T1 total, T2 total and T3 total will be provided as the sum of the number of subjects in each of the subgroups plus any subjects where only T1, T2 or T3 was recorded.
- Gleason total score: Gleason total score from surgery if available, otherwise Gleason total score from biopsy
- Time since adjuvant treatment (months), calculated as [12*(date of informed consent stop date of adjuvant treatment + 1)/365.25]
- Duration of adjuvant treatment (months), calculated as [12*(stop date of adjuvant treatment – start date of adjuvant treatment + 1)/365.25]

- Time since diagnosis of biochemical recurrence (days), calculated as (date of informed consent – date of diagnosis of biochemical recurrence + 1). Time since diagnosis of BCR may be derived in months if more appropriate.
- Baseline PSA value
- Baseline PSA category (0 0.2, >0.2 0.5, >0.5 1, >1 2, >2 5, >5 10 and >10)

In addition, summary table to summarise baseline Prostate Specific Antigen (PSA) by Prior Radical Prostatectomy status (Prior Radical Prostatectomy vs No Prior Radical Prostatectomy) using descriptive statistics (number of subjects (n), mean, standard deviation (SD), minimum, median, and maximum), will be produced.

Details of prostate cancer history will be listed.

Date imputation for incomplete dates:

- If day part missing, put 15th of the month
- If day and month parts missing, put 01 July

4.4.4 Cancer Therapies for Prostate Cancer

Cancer therapies for prostate cancer will be coded according to the World Health Organization Drug Dictionary Enhanced (WHO DDE) (Enhanced) version Sep 2015.

Cancer therapies will be categorised as follows:

Subjects with radical prostatectomy:

- Radiotherapy
- No radiotherapy

Subjects without radical prostatectomy:

- Radiotherapy only
 - o EBRT only
 - Brachytherapy only
 - EBRT and brachytherapy
- Radiotherapy and other therapies
 - EBRT and other therapies
 - Brachytherapy and other therapies
- Other therapies

Prior cancer therapies for prostate cancer are defined as those for which the end date is prior to the date of injection of fluciclovine (¹⁸F).

Concomitant/post-scan cancer therapies for prostate cancer are defined as those with a start date on or after the injection date of fluciclovine (¹⁸F), or those with a start date before the injection date of fluciclovine (¹⁸F) but which continued with a stop on or after the injection date of fluciclovine (¹⁸F). Summaries for subjects with prior and post-scan radical prostatectomy will be presented separately.

Date: 10OCT2018 Version: Amendment 1 Final

Summary table to summarise time from ¹⁸F-fluciclovine PET/CT to first post-¹⁸F-fluciclovine treatment in days using descriptive statistics (number of subjects (n), mean, SD, minimum, median, and maximum) will be provided.

If cancer therapy dates are incomplete and it is not clear whether the medication was concomitant, it will be assumed to be concomitant.

The number and percentage of subjects per category of prostate cancer therapy will be presented for all subjects from the SAF, separately for subjects with and without radical prostatectomy. This summary will be repeated for prior and concomitant cancer therapies.

All therapies for prostate cancer will be listed including type of therapy, reported therapy name, medication class, standardised medication name, dose, dose unit, route of administration, start date and end date or 'ongoing' flag, therapy comments.

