6.2. Inclusion Criteria

- (1) The subject is a male ≥ 18 years old.
- (2) The subject has had an original diagnosis of PCa and underwent radical curative therapy at least 3 months before enrolment, and has been diagnosed with BCR on the basis of:
 - a. Post RRT / brachytherapy: Increase in PSA level ≥ 2.0 ng/mL above the nadir level after radiotherapy (RT) or brachytherapy (ASTRO-Phoenix criteria) [53], or
 - b. Post RP: EITHER two consecutive rises in PSA and final PSA > 0.1 ng/mL OR three consecutive rises in PSA. This definition is also applicable to subjects with PSA persistence post RP (where the PSA fails to fall to undetectable levels).
 - i. In addition, the subject post RP, should have a PSA doubling time of ≤ 15 months OR PSA level ≥ 1.0 ng/mL at time of recruitment. The PSA doubling time will be calculated using the Memorial Sloan Kettering Cancer Center nomogram (<http://www.mskcc.org/nomograms/prostate/psa-doubling-time>), based on a minimum of two PSA levels within 12 months of screening, taken after the last recorded nadir PSA available at time of screening.
- (3) The subject has not had previous recurrences of PCa, i.e. this is the first diagnosis of BCR.
- (4) The subject is being considered for radical salvage therapy.
- (5) The subject is able and willing to comply with study procedures, and signed, dated and timed informed consent is obtained before any study-related procedure is performed.
- (6) The subject's Eastern Cooperative Oncology Group [ECOG] performance status 0-2.
- (7) The subject should not have received androgen-deprivation therapy within 3 months of screening.
- (8) The subject has a normal or clinically acceptable medical history and vital signs findings at screening (up to 14 days before administration of study drug).

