The number, percentage and exact 95% CI of subjects with and without a change in management plan after the fluciclovine (18F) scan results become available will be presented. In addition, the number and percentage of subjects with changes categorised as major or other will be presented. These summaries will be repeated separately for subjects with a positive and a negative fluciclovine (18F) scan and for subjects without prostatectomy and with prostatectomy.

Date: 10OCT2018 Version: Amendment 1 Final Page 17 of 22

The number, percentage and 95% CI of subjects who agreed to the revised management plan after fluciclovine (¹⁸F) scan results become available will be presented.

Details of the intended management plan, revised management plan and agreed management plan will be listed.

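### SAP 4.4.3 imputes partial dates with no bound at consent, so time since recurrence and the adjuvant intervals can be zero or negative; the therapy-date default in 4.4.4 should also use the entry limits

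*SAP*

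**What the plan says.** **Partial dates (SAP 4.4.3).** Time since BCR is consent date minus BCR date plus 1, in days. Time since adjuvant treatment and adjuvant duration are built the same way and converted to months. A missing day becomes the 15th. For year-only dates the rule is "If day and month parts missing, put 01 July". No upper bound, lower bound or ordering of dates is stated. SAP section 2 allows imputation of partial dates and leaves the detail to each section, so it adds no bound either.

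**Entry limits (Protocol 6.2).** A subject "underwent radical curative therapy at least 3 months before enrolment, and has been diagnosed with BCR on the basis of" stated PSA criteria. Also, "The subject should not have received androgen-deprivation therapy within 3 months of screening".

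**Therapy class (SAP 4.4.4).** "Prior cancer therapies for prostate cancer are defined as those for which the end date is prior to the date of injection". "Concomitant/post-scan cancer therapies for prostate cancer are defined as those with a start date on or after the injection date", or a start before injection with a stop on or after it. For partial dates: "If cancer therapy dates are incomplete and it is not clear whether the medication was concomitant, it will be assumed to be concomitant". The section also asks for a "Summary table to summarise time from ¹⁸F-fluciclovine PET/CT to first post-¹⁸F-fluciclovine treatment in days".

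**Split of the primary result (SAP 5.4.1).** The summaries are repeated "for subjects without prostatectomy and with prostatectomy", without the word prior. SAP 4.4.3 does use that word for its PSA table, and 4.4.4 presents prior and post-scan prostatectomy separately.

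**The concern.** A mid-period imputation is reasonable only if the result stays inside what is already known. Here two things are known: BCR was diagnosed by the time of consent, and a course of treatment cannot stop before it starts. The rule in 4.4.3 uses neither, so when followed exactly it can put impossible values into the time-since-BCR, time-since-adjuvant and adjuvant-duration summaries. The minimum is the most visible casualty; the mean and SD move too.

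The therapy default has a related weakness. The same default appears for ordinary medication in SAP 4.4.5, where concomitant means only concomitant. In 4.4.4 the class also holds treatment that follows from the scan. An old radical treatment or an earlier course of androgen-deprivation therapy (ADT) with a poor stop date could be counted there, although eligibility shows that it ended before the scan.

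**Working it through.** The documents give no figure for this point, so there is none to reproduce. The check applies the stated formulas to possible dates. The years 2016 and 2017 are assumed, as one leap and one ordinary year.

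**1. Time since BCR, day missing, BCR in the consent month.** Value = consent day - 15 + 1 = consent day - 14.
- Consent on the 1st: 1 - 14 = -13 days (minimum).
- Consent on 5 March: 5 - 14 = -9 days. The true value lies between 1 and 5.
- Negative for consent on days 1 to 13 (13 × 12 = 156 dates a year) and zero on day 14 (12 dates). In all, 168 of 365 or 366 consent dates fall below the true minimum of 1.

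**2. Time since BCR, year only, BCR in the consent year.** Value = consent date - 1 July + 1.
- Consent 10 February 2016: -142 + 1 = -141 days.
- Consent 1 January 2017: -181 + 1 = -180 days. Consent 1 January 2016: -182 + 1 = -181 days.
- Negative for consent from 1 January to 29 June (180 of 365 dates, or 181 of 366) and zero on 30 June.

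**3. Adjuvant intervals.**
- Time since adjuvant treatment, consent 1 April 2016, stop known only as 2016: 12 × (-91 + 1)/365.25 = -3.0 months.
- Adjuvant duration, start 1 September 2014, stop known only as 2014: -62 + 1 = -61 days, or 12 × (-61)/365.25 = -2.0 months.
- Start and stop both known only as the same year: 12 × 1/365.25 = 0.03 months, whatever the true length.

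**4. Effect of one such record on a mean.** For consent on 10 February 2016, the true time since a 2016 BCR is 1 to 41 days, so -141 is wrong by 142 to 182 days. The size of the full analysis set is not stated. Taking 85 (interim size) and 180 (planned size) as a range, one record lowers the mean by 142/180 = 0.8 to 182/85 = 2.1 days and makes the reported minimum negative.

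**5. Effect of a cap.** With the imputed BCR date set to the earlier of the imputed date and consent, the smallest value over all consent dates is 1 day under both rules.

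**6. Therapy class.** Take 365 consent dates in each of the two years, the scan 0 or 14 days after consent (Protocol Appendix A allows up to 14), and radical therapy ending at least 3 months before consent.
- End month known: the latest eligible end month is over before consent. 0 of 730 consent dates leave the class unclear.
- End year only: an eligible therapy can share the scan's calendar year for 549 of 730 consent dates (scan same day) or 522 of 730 (scan 14 days later). The partial date alone then does not settle the class.
- End date wholly missing: the date never settles it.

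The 3-month limit on ADT gives the same result for ADT before entry. If the entry limits are used, none of these records reaches the default in eligible subjects.

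**The case against.** Much can be said on the other side, and part of it stands.

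- **Year-only BCR dates should be rare.** Recurrence is defined by PSA, and Protocol 7.5 has dated PSA values and the BCR date taken from hospital records. That stands for the year-only case. A missing day in the consent month is more plausible, and there the error is at most about two weeks.
- **The default in 4.4.4 is conditional.** It applies only where status is not clear, and an analyst could reason that eligibility makes it clear. The SAP does not forbid this, but it does not say so either; its classes are defined by dates alone.
- **The entry limits reach only so far.** They cover radical therapy and ADT. Other adjuvant treatment, such as radiotherapy, is not named. The therapy table uses the safety set, which may include ineligible subjects.

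A reader might infer more: that old treatment will be counted as post-scan treatment, that it then enters the PSA response by treatment administered (SAP 5.4.2.1) and makes time to first treatment negative, and that the primary split conditions on surgery chosen after the scan. The documents do not support this. The trigger is narrow, since a known end month is enough. No text links the combined class to treatment administered. The time table concerns the first treatment after the scan, which a therapy begun before it is not, and Protocol 7.7 has the management start date recorded at Visit 6. Prior status is the natural reading of the prostatectomy split, given how 4.4.3 and 4.4.4 use the term.

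**Conclusion.** The concern holds for SAP 4.4.3. Applied as written, the imputation rule yields values that the entry criteria rule out: down to -13 days with the day missing, down to -180 or -181 days with year only, and negative adjuvant intervals. This is a wrong result from a stated rule, not a missing detail.

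For SAP 4.4.4 the point is secondary. The default can misplace an eligible subject's radical therapy or pre-entry ADT only if the end date is year-only in the scan year or wholly missing, and only if the analyst does not apply eligibility. In SAP 5.4.1 the missing word is a matter of consistency.

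The date rules affect descriptive tables only. The primary endpoint compares recorded plans and uses none of these dates. The number of incomplete dates is not given, so the size in the actual data is unknown and may be nil. This is a minor improvement.

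**What to change.** **SAP 4.4.3 (main change).**
- Cap an imputed date at the informed consent date. If the recorded part already lies after consent, query it rather than cap it.
- Keep an imputed stop on or after the start.
- Do not compute adjuvant duration when a month is missing.

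**SAP 4.4.4.**
- Define post-scan therapy by a start date on or after injection.
- In eligible subjects, class as prior a radical therapy or pre-entry ADT record that is not flagged ongoing and whose end date is year-only in the scan year or wholly missing, unless the known part of the date shows that it continued past injection. That exception is needed: a blanket rule sending every pre-scan start with an incomplete stop to prior would misclass a therapy stopped in March 2017 after a January 2017 scan.
- Leave other adjuvant therapy under the present default, since the entry criteria do not bound it.

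**SAP 5.4.1.** Write prior prostatectomy, in line with 4.4.3.

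**Cost.** A few sentences and minor programming. A few adjuvant durations become missing instead of imputed. A capped date is still an imputation, and it pulls time since BCR to 1 day, so the number of imputed dates should be footnoted. The bounds rest on the entry criteria, consent and date order, not on outcomes, so they could be added by addendum, as the SAP has already done after database lock, without raising doubt about result-driven choices.

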4.4.5 Prior and Concomitant Medications

Prior and concomitant medications will be coded according to the World Health Organization Drug Dictionary Enhanced (WHO DDE) (Enhanced) version Sep 2015.

Prior medications are defined as those for which the end date is prior to the date of injection of fluciclovine (18F).

Concomitant medications are defined as those with a start date on or after the injection date of fluciclovine (¹⁸F), or those with a start date before the injection date of fluciclovine (¹⁸F) but which continued with a stop date on or after the injection date of fluciclovine (¹⁸F).

If medication dates are incomplete and it is not clear whether the medication was concomitant, it will be assumed to be concomitant.

The number and percentage of subjects who took any medications will be presented by centre and overall by medication class, standardised medication names sorted alphabetically for all subjects from the SAF, separately for prior medications and concomitant medications.

All prior and concomitant medications will be listed including reported name, medication class, standardised medication name, indication, dose, dose unit, frequency, route of administration, start date and end date or 'ongoing' flag.

4.5 Administration of Investigational Product

The volume of undiluted fluciclovine, activity of fluciclovine and injection site reaction during and following fluciclovine administration will be summarised for subjects in the SAF.

5 EFFICACY EVALUATION

All listings will be based on the FAS unless specified otherwise. The primary efficacy analysis will be based on the EAS and will be repeated on the PPS as a secondary analysis. The secondary efficacy analyses will be based on the FAS.

Date: 10OCT2018 Version: Amendment 1 Final

5.1 **Primary Efficacy Variable**

The primary efficacy variable is the record of the revised management plan post fluciclovine (¹⁸F) PET/CT scan in comparison to the pre-scan intended management plan.

5.2 **Secondary Efficacy Variables**

The secondary efficacy variables are:

- The proportion of subjects who have a sustained response to radical salvage therapy.
- PSA levels in relation to scan positivity will be analysed to determine the optimal PSA threshold for detecting recurrent PCa by fluciclovine (18F) PET/CT.

Definition of Region Levels

Two main regions will be analysed, the prostate and prostate bed and the extraprostatic region.

The prostate and prostate bed include the following lesion locations:

- Prostate bed left
- Prostate bed right
- Peripheral zone left
- Peripheral zone right
- Central gland left
- Central gland right
- Left seminal vesicle
- Right seminal vesicle

The extra-prostatic regions include the following lesion locations

- Lymph nodes
 - Pelvic lymph nodes
 - Common iliac left
 - Common iliac right
 - Internal iliac left
 - Internal iliac right
 - External iliac left
 - External iliac right
 - Obturator left
 - Obturator right
 - Pre-sacral left

- Pre-sacral right
- Peri-rectal anterior
- Peri-rectal posterior
- Peri-rectal left
- Peri-rectal right
- Inguinal left
- Inguinal right

Date: 10OCT2018 Version: Amendment 1 Final ST/form/010/6

- Retroperitoneal lymph nodes
 - Para-aortic
 - Retro-aortic
 - Para-caval
 - Retro-caval
- Other lymph nodes
 - Intra-peritoneal
 - Mediastinal left
 - Mediastinal right
 - Axillary left
- Soft tissues/parenchyma
 - o Lung upper lobe left
 - Lung upper lobe right
 - Lung middle lobe right
 - Lung lower lobe left
 - o Lung lower lobe right
 - Brain left
 - o Brain right
 - Liver left
 - Liver right
 - Spleen
 - Subcutaneous/cutaneous
 - Muscle
 - Bowel
- Bones
 - o Skull
 - Skull base/maxilla left
 - Skull base/maxilla right
 - Mandible left
 - Mandible right
 - Vertebra
 - Vertebra C1
 - Vertebra C2
 - Vertebra C3
 - Vertebra C4

- Aorto-caval
- Retrocrural left
- Retrocrural right
- Axillary right
- Cervical left
- Cervical right

Vertebra C5

Vertebra C6

Vertebra C7

Vertebra T1

Date: 10OCT2018 Version: Amendment 1 Final ST/form/010/6

- Vertebra T2
- Vertebra T3
- Vertebra T4
- Vertebra T5
- Vertebra T6
- Vertebra T7
- Vertebra T8
- Vertebra T9
- Vertebra T10
- Vertebra T11

o Chest

- 1st rib left
- 1st rib right
- 2nd rib left
- 2nd rib right
- 3rd rib left
- 3rd rib right
- 4th rib left
- 4th rib right
- 5th rib left
- 5th rib right
- 6th rib left
- 6th rib right
- 7th rib left
- 7th rib right
- 8th rib left

Pelvis

- Ilium left
- Ilium right
- Superior pubic ramus left
- Superior pubic ramus right
- Inferior pubic ramus left

- Vertebra T12
- Vertebra L1
- Vertebra L2
- Vertebra L3
- Vertebra L4
- Vertebra L5
- Sacrum left
- Sacrum right
- Sacrum central
- 8th rib right
- 9th rib left
- 9th rib right
- 10th rib left
- 10th rib right
- 11th rib left
- 11th rib right
- 12th rib left
- 12th rib right
- Sternum
- Clavicle left
- Clavicle right
- Scapula left
- Scapula right
- Inferior pubic ramus right
- Pubic body left
- Pubic body right
- Ischium left
- Ischium right

Version: Amendment 1 Final ST/form/010/6

Appendicular

- Proximal humerus left
- Proximal humerus right
- Proximal femur left
- Proximal femur right

